2.2 Trial Design

2.2.1 Summary of Trial Design

This is an open-label, two stage, single arm pivotal study of intravenous (IV) pembrolizumab in patients with advanced or metastatic uveal melanoma. The primary endpoint of the study will be objective response rate (ORR). Other endpoints include progression-free survival (PFS), overall survival (OS), response duration, safety, and correlation of response rate with biomarkers (GNAQ/GNA11 mutational status, PD-L1 expression).

The study will enroll 10 patients in stage I of this two stage design; if one or more responses occur, an additional 19 patients will be enrolled. The sample size was designed to test whether pembrolizumab has a $\geq 20\%$ response rate in uveal melanoma with a clinically uninteresting response rate of 5%. In addition, if ≥ 2 patients experience stable disease (SD) for > 24 weeks, then the study may proceed to stage 2 if the sponsor and PIs are in agreement.

The primary objective of the study is to evaluate the activity of pembrolizumab in terms of ORR. The overall type I error rate for this study is strictly controlled at 5% (two-sided) and the study has a power of 80%. The study is considered to be positive if at least 4 patients treated with pembrolizumab have an objective response (of 29 subjects enrolled). All patients receiving pembrolizumab will receive pembrolizumab as IV infusion at a dose of 200mg every 3 weeks until disease progression, intolerable toxicity, confirmed complete response,

withdrawal of consent, or they require another form of antineoplastic therapy as determined by the Investigator.

We anticipate an accrual rate of 1 to 2 patients per month from 3 participating centers.

After the baseline tumor evaluation, tumor assessment during the study will be performed by radiological scans every 6 weeks starting from Week 12 until Week 24. At the discretion of investigators, patients who remain on study after 24 weeks and are clinically stable may decrease imaging frequency to every 12 weeks in the following schedule:

- First scheduled disease assessment: week 12
- Disease assessments every 6 weeks from week 18-24
- Disease assessments every 12 weeks from week 36-96

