5.5.2 Prohibited Concomitant Medications

Subjects are prohibited from receiving the following therapies during the Screening and Treatment Phase (including retreatment for post-complete response relapse) of this trial:

- Anti-cancer systemic chemotherapy or biological therapy
- Immunotherapy not specified in this protocol
- Chemotherapy not specified in this protocol
- Investigational agents other than pembrolizumab
- Radiation therapy
 - Note: Radiation therapy to a symptomatic solitary lesion or to the brain may be allowed after consultation with Sponsor.
- Live vaccines within 30 days prior to the first dose of trial treatment and while participating in the trial. Examples of live vaccines include, but are not limited to, the following: measles, mumps, rubella, chicken pox, yellow fever, rabies, BCG, and typhoid (oral) vaccine. Seasonal influenza vaccines for injection are generally killed virus vaccines and are allowed; however intranasal influenza vaccines (e.g. Flu-Mist®) are live attenuated vaccines, and are not allowed.
- Glucocorticoids for any purpose other than to modulate symptoms from an event of clinical interest of suspected immunologic etiology. The use of physiologic doses of corticosteroids may be approved after consultation with the Sponsor.

Subjects who, in the assessment by the investigator, require the use of any of the aforementioned treatments for clinical management should be removed from the trial. Subjects may receive other medications that the investigator deems to be medically necessary.

The Exclusion Criteria describes other medications which are prohibited in this trial.

Protocol date: August 30, 2016

Confidential

There are no prohibited therapies during the Post-Treatment Follow-up Phase.

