7.1.3.3 Response Criteria (irRC)

7.1.3.3.1 Immune-related RECIST Criteria (irRECIST) Overview

- All measurements are undimensional
- If a patient is classified as having progressive disease, confirmation by a second scan at least 4 weeks later in the absence of rapid clinical deterioration is required to assess for a late response.
- The presence of new lesions does not constitute disease progression by itself.
- Target lesions and new lesions are incorporated into overall tumor burden which is used to evaluate progression or responses as in the following:

Tumor Burden = Sum of the Diameter (target) + Sum of the Diameter (new)

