7.1.3.3.5 Evaluation of Overall Response

Table 8 Evaluation of Overall Response for Subjects with Measurable Disease at Baseline

Overall Response	irRECIST (total tumor burden = target lesions + new lesions)	Non-target lesions	New lesions
irCR	Disappearance of all lesions	Absence	Absence
irPR	≥ 30% decrease in tumor burden compared with baseline	Any	Any
irSD	<30% decrease to < 20% increase in total tumor burden compared with baseline	Any	Any
irPD	≥ 20% increase in tumor burden compared with nadir or baseline with confirmation of progression by a second scan at least 4 weeks later	Any	Any

ir=immune related, CR=complete response, PR = partial response, SD=stable disease, PD=progressive disease, NA= Not applicable, and NE=Not Evaluable

NOTE:

- Subjects with a global deterioration of health status requiring discontinuation of treatment without objective evidence of disease progression at that time should be classified as having "symptomatic deterioration." Objective response status is determined by evaluations of disease burden. Every effort should be made to document the objective progression even after discontinuation of treatment.
- In some circumstances, it may be difficult to distinguish residual disease from normal tissue. When the evaluation of CR depends on this determination, it is recommended that the residual lesion be investigated (fine needle aspirate/biopsy) to confirm the CR.
- If patients experience irPD and remain clinically stable or improved, an exception may be granted to continue on study after discussion with the PI. If confirmed irPD is documented and an exception is granted, repeat imaging should be performed in 4-6 weeks and if further progression is documented then study treatment should be discontinued. If an isolated lesions progresses and is treated with local therapy (surgical resection or radiation therapy), imaging should be performed to document local stability and overall irRECIST re-evaluation.

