9.0 STATISTICAL ANALYSIS PLAN

9.1 Statistical Analysis Plan Summary

The primary objective is to determine whether pembrolizumab is an effective therapy in uveal melanoma. The null hypothesis is that the objective response rate (ORR; percentage of patients achieving a confirmed CR or PR) is not attractive (defined as $\leq 5\%$). The alternative hypothesis is that the response rate is of interest for further development (defined as $\geq 20\%$).

Product: MK-3475
Protocol/Amendment No. 03

The final analysis of the overall response rate will be performed with a power of 80% with one sided $\alpha=0.05$. It is calculated that at least 4 responses are needed out of a total of 29 patients to reject the null hypothesis.

To allow early termination of the trial due to lack of efficacy, the trial will be conducted in two stages per Simon's Optimal Design. If no responses are demonstrated in the first 10 patients, then the trial will be terminated early for futility. If ≥ 1 responses are observed, enrollment will continue to 29 patients. Notably, in the absence of ≥ 1 response, if ≥ 2 patients experience stable disease (SD) for >24 weeks, then the study may proceed to stage 2 if the sponsor and PIs are in agreement. This provision was added since the probability of early termination was as high as 10% even with a response rate of 20%.

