9.2.2 Efficacy Endpoints

9.2.2.1 Primary Endpoint

Objective response rate (ORR) as defined by immune-related response criteria (irRC) will be the primary endpoint of the study. As mentioned, the primary hypothesis is that ORR of pembrolizumab in uveal melanoma will be 20%. We will enroll 10 patients in stage I to allow for early termination for futility. If no responses are observed the trial will be terminated. However, if ≥ 1 objective response occurs, OR if ≥ 2 patients experience stability of disease for ≥ 24 weeks, the trial will proceed to stage II.

Product: MK-3475

Protocol/Amendment No. 03

In stage II, an additional 19 patients will be enrolled. If ≥ 4 responses occur in all patients treated on stage I and stage II, the trial will be considered positive.

Of note, response rates by RECIST 1.1 criteria will also be assessed although irRC will be used for the primary endpoint.

ORR will be stratified by PD-L1 expression and *GNAQ/GNA11* mutation status (see section 8.2.2.3).

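### Nothing in the plan stops tumour shrinkage produced by resecting or irradiating a lesion from being scored as a confirmed irPR and counted among the four responses that make the trial positive.

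*Combined protocol and SAP*

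**What the plan says.** **How response is measured.** Section 7.1.3.3.1 defines the quantity as "Tumor Burden = Sum of the Diameter (target) + Sum of the Diameter (new)". Section 7.1.3.3.2 and Table 8 define irPR as a fall of at least 30% in that sum from baseline, whatever the status of non-target and new lesions. Section 7.1.3 asks for a confirming scan at least 4 weeks later.

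**Local therapy.** The last note in section 7.1.3.3.5 says that when an isolated lesion progresses and is "treated with local therapy (surgical resection or radiation therapy), imaging should be performed to document local stability and overall irRECIST re-evaluation". It stops there.

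**Scoring of a lesion that is no longer there.** Section 7.1.3.3.2 has two relevant notes. A lesion judged likely to have disappeared is entered as 0 mm. If not all baseline targets are assessed, no sum can be calculated for CR, PR or SD. Neither note mentions resection or radiation.

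**Local therapy as a concomitant treatment.** Section 5.5.2 prohibits radiation and says that subjects who need a prohibited treatment should come off the trial. It makes an exception: "Radiation therapy to a symptomatic solitary lesion or to the brain may be allowed after consultation with Sponsor". Surgery is not on the list.

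**The decision rule.** Section 9.1 counts confirmed CR or PR. Section 9.2.2.1 says that if four or more "responses occur in all patients treated on stage I and stage II, the trial will be considered positive". Neither section mentions local therapy.

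**The concern.** Resecting a target lesion lowers the sum of diameters mechanically, and irradiating it may lower the sum for reasons unrelated to the study drug. The plan asks for an overall irRECIST re-evaluation after the procedure, and the ordinary definitions are the only ones available for it. Followed literally, they can return irPR, and a scan 4 weeks later would confirm it.

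Prior progression does not necessarily block this. irPD needs a confirming scan. Under section 7.1.3, if that scan shows response or stable disease relative to baseline, treatment continues or resumes. A lesion removed before the confirming scan could therefore leave the irPD unconfirmed. Where irPD is confirmed, section 7.1.3.3.5 still lets an exception be granted.

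At stake is the primary decision. The threshold is four responses, and assessment is open-label by the investigator with site radiology reading, so one misattributed response carries weight. In stage 1 it would also open stage 2 by itself. A post-procedure irSD could feed the alternative 24-week stable-disease route into stage 2.

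**Working it through.** **1. The plan's own figure.** Inputs from sections 9.1 and 9.2.1: null rate 5%, alternative 20%, 10 patients in stage 1, stop at 0 responses, 19 more in stage 2, positive at 4 or more of 29.

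P(positive) = Σ over x ≥ 1 of P(X₁ = x) × P(X₂ ≥ 4 − x), with X₁ ~ Bin(10, p) and X₂ ~ Bin(19, p).

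At p = 0.05: 0.3151 × 0.0665 + 0.0746 × 0.2453 + 0.0105 × 0.6226 + 0.0010 = 0.0468. Table 11 gives 0.047. At p = 0.20 the result is 0.801, as stated; the other four rows also reproduce. Section 2.2.1 says the type I error "is strictly controlled at 5% (two-sided) and the study has a power of 80" percent, whereas section 9.1 calls it one-sided. The calculation matches one-sided; that is a separate point. All figures below ignore the stable-disease route unless noted.

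**2. Can local therapy produce irPR?** Hypothetical case: baseline targets 30 + 25 + 25 = 80 mm.
- The first grows to 50 mm: sum 100 mm, (100 − 80)/80 = +25%, irPD.
- It is resected and entered as 0 mm: sum 50 mm, (50 − 80)/80 = −37.5%, irPR.

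If the other targets are unchanged, the treated lesion must have made up at least 30% of the baseline sum. One of five equal targets gives −20% and one of four gives −25%; neither is irPR. Removing a measured new lesion only returns the sum to the remaining targets, so it yields irPR only if those have already shrunk by 30%. Non-target lesions are outside the sum.

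**3. Effect of exactly one false response, given that it occurs, at p = 0.05.**

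*Patient in stage 2* (10 others in stage 1, 18 in stage 2):
- Scored as a false response: Σ over x ≥ 1 of P(X₁ = x) × P(Bin(18) ≥ 3 − x) = 0.3151 × 0.2265 + 0.0746 × 0.6028 + 0.0105 + 0.0010 = 0.128.
- Same patient scored as a non-responder: 0.3151 × 0.0581 + 0.0746 × 0.2265 + 0.0105 × 0.6028 + 0.0010 = 0.043.

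*Patient in stage 1* (stage 2 opens automatically, so 3 more are needed among 28):
- False response: 1 − (0.2378 + 0.3505 + 0.2490) = 0.163.
- Non-responder: Σ over x ≥ 1 of P(Bin(9) = x) × P(Bin(19) ≥ 4 − x) = 0.041.

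The differences are 0.128 − 0.043 = 0.085 and 0.163 − 0.041 = 0.122, about 9 to 12 trials in 100.

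**4. Overall false-positive rate.** If each non-responder has probability q of a false irPR, the effective rate is 0.05 + 0.95q. The documents give no value for q, so the whole column is an assumption. Expected false responders in a full 29 patients are 29 × 0.95 × q.

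| q | Effective rate | P(positive) | Expected false responders in 29 |
|---|---|---|---|
| 0 | 0.0500 | 0.047 | 0 |
| 0.1% | 0.0510 | 0.050 | 0.03 |
| 0.25% | 0.0524 | 0.054 | 0.07 |
| 0.5% | 0.0548 | 0.061 | 0.14 |
| 1% | 0.0595 | 0.078 | 0.28 |
| 2% | 0.0690 | 0.118 | 0.55 |
| 3% | 0.0785 | 0.165 | 0.83 |
| 5% | 0.0975 | 0.274 | 1.38 |

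**5. The stable-disease route.** It adds no response. If it always let the trial continue, the rate with no false responses would be P(Bin(29, 0.05) ≥ 4) = 0.055, which bounds its effect.

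**The case against.** The strongest reply is that the text already limits this.

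- *The not-assessed note in section 7.1.3.3.2.* A resected target can reasonably be read as not assessed, which would make the time point not evaluable for response. This stands as a possible reading. But an imaged, empty resection site also fits the 0 mm note, and an irradiated lesion can still be measured. The section is ambiguous on resection and offers no bar for radiation.
- *Section 5.5.2.* Radiation is prohibited by default and removal from the trial follows. The exception for a symptomatic solitary lesion overlaps with the isolated lesion of section 7.1.3.3.5, and surgery is not listed.
- *Confirmed progression.* Sections 5.8, 7.1.3 and 7.1.6.4.1 end treatment and move the patient to telephone survival follow-up. That removes many candidates, but section 7.1.3.3.5 allows exceptions.
- *Rarity.* The route needs a dominant target, a patient who stays under assessment, no offsetting growth elsewhere, and a confirming scan. This stands, and it is why the low end of the table matters as much as the high end.

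A reader might infer that the plan tells sites to credit pembrolizumab with the effect of surgery. It does not. The sentence closes a note on staying on study after irPD and is silent on scoring; the defect is that silence.

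**Conclusion.** The gap is real: the plan calls for re-evaluation after local therapy and has no rule that keeps the resulting shrinkage out of the primary count. It should be closed before analysis, though few patients are likely to be affected.

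Two stronger readings are not supported. First, 0.13 and 0.16 might be taken as the trial's type I error. They are conditional on a false response having occurred; the design's own figure of 0.047 is correct for the inputs it states. Second, with a threshold of four, one false response might be called decisive. It changes the outcome in about 9 to 12 trials in 100 at a 5% true rate.

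The unconditional effect depends entirely on q. At 0.1% to 0.5% the false-positive rate is 0.050 to 0.061, close to nominal. At 5%, which implies more than one false responder per full trial, it is 0.27. Nothing in the documents locates q within that range. The calculation also assumes independent patients and the 0-of-10 stopping rule.

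**What to change.** Add one rule to sections 9.2.2.1 and 7.1.3.3.5:

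- Best overall response, and stable disease for the stage 1 decision, use only assessments made before any resection or irradiation of a target or measured new lesion. A response and its confirming scan must therefore both precede the procedure.
- Later time points are not evaluable for CR, PR and SD.
- Post-procedure irRECIST status is reported separately as a sensitivity analysis.

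This also settles the ambiguity between the two notes in section 7.1.3.3.2. It governs only which assessments count and changes no patient's care. With the rule in place, the binomial input is again response before local therapy, and the stated 0.047 and 0.801 apply under the 0-of-10 stopping rule.

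Separately, reconcile section 5.5.2 (radiation prohibited, with removal from the trial apart from the exception) with section 7.1.3.3.5 (local therapy followed by re-evaluation), and say where surgery falls.

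Cost: one SAP rule and a lesion-level flag with the date of local therapy on the case report form. The downside is that a genuine drug response first seen after local therapy would not count in the primary analysis; the sensitivity analysis would show it.

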7.1.4 Laboratory Procedures/Assessments

Details regarding specific laboratory procedures/assessments to be performed in this trial are provided below.

7.1.4.1 Laboratory Safety Evaluations (Hematology, Chemistry and Urinalysis)

Laboratory tests for hematology, chemistry, urinalysis, and others are specified in Table 9.

Table 9 Laboratory Tests

Hematology	Chemistry	Other
Hematocrit	Albumin	Serum β -human chorionic gonadotropin†
Hemoglobin	Alkaline phosphatase	(β -hCG)†
Platelet count	Alanine aminotransferase (ALT)	PT (INR)
WBC (total and differential)	Aspartate aminotransferase (AST)	aPTT
Red Blood Cell Count	Lactate dehydrogenase (LDH)	Total triiodothyronine (T3)
Absolute Neutrophil Count	Carbon Dioxide ‡ (CO₂ or bicarbonate)	Free tyroxine (T4) Thyroid stimulating hormone (TSH)
	Uric Acid	
	Calcium	
	Chloride	Blood for correlative studies
	Glucose	
	Potassium	
	Sodium	
	Magnesium	
	Total Bilirubin	
	Direct Bilirubin (If total bilirubin is elevated above the upper limit of normal)	
	Total protein	
	Blood Urea Nitrogen	

† Perform on women of childbearing potential only. If urine pregnancy results cannot be confirmed as negative, a serum pregnancy test will be required.

‡ If considered standard of care in your region.

Laboratory tests for screening or entry into the Second Course Phase should be performed within 14 days prior to the first dose of treatment. After Cycle 1, pre-dose laboratory procedures can be conducted up to 72 hours prior to dosing. Results must be reviewed by the investigator or qualified designee and found to be acceptable prior to each dose of trial treatment.

7.1.5 Other Procedures

7.1.5.1 Withdrawal/Discontinuation

When a subject discontinues/withdraws prior to trial completion, all applicable activities scheduled for the final trial visit should be performed at the time of discontinuation. Any adverse events which are present at the time of discontinuation/withdrawal should be followed in accordance with the safety requirements outlined in Section 7.2 - Assessing and Recording Adverse Events. Subjects who a) attain a CR or b) complete 24 months of treatment with pembrolizumab may discontinue treatment with the option of restarting treatment if they meet the criteria specified in Section 7.1.6.2.2. After discontinuing treatment following assessment of CR, these subjects should return to the site for a Safety Follow-up Visit (described in Section 7.1.6.3) and then proceed to the Follow-Up Period of the study (described in Section 7.1.6.4).

7.1.5.2 Blinding/Unblinding

No blinding will be performed in this trial.

7.1.6 Study Visits

Study procedures should be performed as close to the scheduled time as possible. The exact time at which a procedure is performed must be recorded in the patients study records or appropriate worksheet (if applicable). Any nonscheduled procedures required for urgent evaluation of safety concerns take precedence over all routine scheduled procedures.

A detailed outline of all scheduled study procedures is provided in the Study Flow Chart (Section 6.0). Procedures should be performed at the study center where the patient is being treated.

Blood collections for safety evaluation assume priority over other procedures. Whenever possible, blood samples should be obtained by fresh peripheral venipuncture. If a patient does not have peripheral access, the sample may be collected from a central catheter immediately after an initial withdrawal of at least 10 mL of blood; or preferably, after a series of other blood sample collections from the central catheter.

The patient will be assessed for adverse experiences per the Study Flow Chart (Section 6.0) and at all unscheduled visits.

Specific procedure-related details are provided above in Section 7.1 - Trial Procedures.

7.1.6.1 Screening Period

All screening procedures will be performed during the screening period. Screening requirements are outlined in Section 6.0 - Trial Flow Chart.

7.1.6.2 Treatment Period

7.1.6.2.1 Initial Treatment Period

Treatment visits will occur every 3 weeks with symptom evaluation, physical exam, and laboratory studies as documented in Section 6.0. If grade 3-4 adverse events that meet the criteria listed in Table 3, then the treatment interval may be lengthened to every 4 weeks.

7.1.6.2.2 Subsequent Treatment Period

Patients who stop pembrolizumab with SD or better may be eligible for up to one year of additional pembrolizumab therapy if they progress after stopping pembrolizumab. The following criteria must be met to be eligible for second-course treatment:

- Patient had a confirmed CR and stopped pembrolizumab treatment after at least 6 months plus an additional 2 doses of study therapy OR
 - Patient had SD, PR or CR and stopped pembrolizumab treatment after at least 12 months of study therapy
- Patient has documented disease progression after stopping pembrolizumab study treatment
- Patient did not discontinue pembrolizumab due to AEs from study treatment
- Patient did not initiate new anti-cancer treatment since stopping pembrolizumab (note – local surgery or radiation therapy with palliative intent may be allowed).
- Have a performance status of 0 or 1 on the ECOG Performance Scale
- Demonstrate adequate organ function as detailed in Section 5.1.2
- Female patient of childbearing potential should have a negative urine or serum pregnancy test within 72 hours prior to receiving retreatment with study medication.
- Female patients of childbearing potential should be willing to use 2 methods of birth control or be surgically sterile, or a barrier method plus a hormonal method of contraception to prevent pregnancy, or abstain from heterosexual activity for the course of the study through 120 days after the last dose of study medication (Reference Section 2.2). Patients of child bearing potential are those who have not been surgically sterilized or have been free from menses for > 18 months (see Section 2.2).

- Male patients should agree to use an adequate method of contraception starting with the first dose of study therapy through 120 days after the last dose of study therapy.
- Does not have a history or current evidence of any condition, therapy, or laboratory abnormality that might interfere with the patient's participation for the full duration of the trial or is not in the best interest of the patient to participate, in the opinion of the treating investigator.

Patients who restart treatment will be retreated at the dose and dose frequency they received upon initial treatment with pembrolizumab. Treatment will be administered for up to 12 additional months.

See Section 5.1.2.5 for eligibility requirements for reinduction and Section 6.2 for flowchart for induction.

